Subjects should abstain from taking any herbal and dietary supplements within 5 half lives (or 14 days if the drug is a potential enzyme inducer) prior to the first dose of either study drug until completion of the follow-up visit, unless in the opinion of the Investigator and sponsor there is little concern for a potential drug-drug interaction with the study drug(s). These herbal medications include, but are not limited to, St. John's wort, kava, ephedra (ma huang), ginkgo biloba, dehydroepiandrosterone (DHEA), yohimbe, saw palmetto, and ginseng. The investigator should contact a Medical Monitor before initiating treatment with any herbal preparation.

5.4 **Duration of Therapy**

Duration of therapy will depend on individual response, evidence of disease progression and tolerance. In the absence of treatment delays due to adverse events, treatment may continue indefinitely or until one of the following criteria applies:

- Disease progression,
- Intercurrent illness that prevents further administration of treatment,
- Unacceptable adverse event(s),
- Participant decides to withdraw from the study,
- Participant demonstrates an inability or unwillingness to comply with the oral medication regimen and/or documentation requirements
- Pregnancy, or
- General or specific changes in the participant's condition render the participant unacceptable for further treatment in the opinion of the treating investigator.

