6. EXPECTED TOXICITIES AND DOSING DELAYS/DOSE MODIFICATIONS

Dose delays and modifications will be made using the following recommendations. Toxicity assessments will be performed using the revised NCI CTCAE version 4. All appropriate treatment areas should have access to a copy of the CTCAE version 4, which can be downloaded at: http://ctep.cancer.gov.

If possible, symptoms should be managed symptomatically. In the case of toxicity, appropriate medical treatment should be used (including anti-emetics, anti-diarrheals, etc.).

All adverse events experienced by participants will be collected from the time of the first dose of study treatment, through the study and until the final study visit. Participants continuing to experience toxicity at the off study visit may be contacted for additional assessments until the toxicity has resolved or is deemed irreversible.

Dose Level	Trametinib Dose	GSK2141795 Dose
0 → Starting Dose	1.5 mg PO every day	50 mg PO every day
-1	1.0 mg PO every day	25 mg PO every day

NOTE: AEs occurring in participants treated with GSK2141795 + trametinib may be related to 1) overlapping toxicities between the two agents (*e.g.*, rash and diarrhea); 2) toxicities typically associated with trametinib (*e.g.*, visual disturbance) or GSK2141795 (*e.g.*, hyperglycemia or hypoglycemia). However, toxicities associated with individual agents may be potentiated in the combination, or unanticipated AEs may occur.

The dose modifications may involve one or both agents, and should be based on the nature, severity and attributions of the AEs.

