8. CORRELATIVE/SPECIAL STUDIES

8.1 Hypothesis

The further development and study of molecular targeted therapy has revealed that in many cases, the genetic makeup of the tumor can be used to predict response or resistance to treatment with a given therapeutic. The pre-clinical studies of PI3K pathway and MEK inhibitors, suggest that these drugs will have differential effects on tumors harboring different genetic aberrations [35, 36]. The hypothesis of these studies is that cervical cancers harbor high rates of mutations in both PI3K and RAS pathways and that these mutations may make them more susceptible to agents that target these pathways.

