8.6 Analytic Plan

Molecular correlative analyses will be conducted and all patient outcomes: response, PFS, OS and toxicity will be compared between the PIK3CA and RAS-isoform mutated and WT groups using the statistical methodologies specified above; estimating the proportion of participants harboring mutations in both genes is also of interest, as is comparing their outcomes to those in the remainder of the cohort. These analyses are considered exploratory and will not be adjusted for multiple comparisons.

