14.2 Statistical Analysis

The primary objective of this study is estimation of the best objective response rate (CR + PR) per RECIST 1.1. With the planned accrual of 35 participants to this single-arm trial, there is 91% power to detect an improvement in response rate from 0.07 to 0.22 using a one-sided 0.09-level exact binomial test. Therefore, the null hypothesis will be rejected if 5 or more participants respond to combination therapy with GSK1120212 and GSK2141795. The null hypothesis of 0.07 is based on a weighted average of the observed response rates from the 11 cohorts enrolled to GOG 127 and 227 series.

Secondary objectives include progression-free and overall survival, both of which will be estimated by the Kaplan-Meier method. PFS is defined as the time from registration to the study until documented disease progression or death without progression, whichever occurs first. Participants not experiencing a PFS event will be censored at the last date of documented disease evaluation. Overall survival is defined as the time from study registration to the time of death from any cause, with follow-up censored at the last date

known to be alive. Cox's proportional hazards models will be fitted to explore significant predictors of event-time endpoints.

Toxicity data will be tabulated and compared between any groups of interest using Fisher's exact tests, and will be routinely monitored, analyzed and reviewed by the DF/HCC DSMC.

Molecular correlative analyses will be conducted and all patient outcomes: response, PFS, OS and toxicity will be compared between the PIK3CA and RAS-isoform mutated and WT groups using the statistical methodologies specified above; estimating the proportion of participants harboring mutations in both genes is also of interest, as is comparing their outcomes to those in the remainder of the cohort. These analyses are considered exploratory and will not be adjusted for multiple comparisons.

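### The exploratory toxicity comparison between mutation groups uses Fisher's exact test without regard to time on drug, so if the groups' exposure differs it mixes exposure with risk.

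*Combined protocol and SAP*

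**What the plan says.** Section 14.2 sets the method: "Toxicity data will be tabulated and compared between any groups of interest using Fisher's exact tests". It offers no other denominator, so the natural reading is a count of participants who ever had the event. Section 8.6, repeated in 14.2, names the groups: "response, PFS, OS and toxicity will be compared between the PIK3CA and RAS-isoform mutated and WT groups", using the methods already specified. Both sections call these analyses exploratory and waive adjustment for multiple comparisons. Cox models are mentioned only for event-time endpoints, in the paragraph on progression-free and overall survival.

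The observation period follows treatment. Section 6 states: "All adverse events experienced by participants will be collected from the time of the first dose of study treatment", continuing to the final study visit, which the Section 9 calendar puts 21 days (±7) after the last dose. Under Section 5.4, "treatment may continue indefinitely or until one of the following criteria applies"; the criteria include disease progression and unacceptable adverse events.

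Section 8.1 supplies a reason why exposure might differ by group: "these mutations may make them more susceptible to agents that target these pathways".

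No section gives an exposure summary by group, a fixed comparison window, a rate per unit of time, or a time-to-first-event analysis for toxicity.

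**The concern.** A participant on drug for eight months has had more opportunity to record an event than one on drug for two. Fisher's test on ever/never counts treats them alike. If mutated tumours do better, mutated participants stay on treatment longer and accumulate more events at the same monthly risk, and part of any efficacy difference then appears as a mutation-toxicity association.

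The reverse is also possible. Unacceptable toxicity ends treatment, so a group at higher monthly risk may be observed for less time, and the crude comparison may miss the difference.

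What is at stake is the interpretation of an exploratory table. The exploratory label answers multiplicity. It does not answer a systematic difference in observation time.

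**Working it through.** **The plan's own figure.** The plan states no power or size for the toxicity comparison. The only checkable figure nearby is the primary test: "there is 91% power to detect an improvement in response rate from 0.07 to 0.22 using a one-sided 0.09-level exact binomial test", where "the null hypothesis will be rejected if 5 or more participants respond". With 35 participants, P(X ≥ 5) is 0.910 at a response rate of 0.22, which agrees with 91%, and 0.0948 at 0.07, which matches 0.09 only when rounded. This confirms the design inputs and does not bear on the present point.

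**Inputs.**
- Group sizes: 35 × (31.3% PIK3CA + 8.8% KRAS) = 14.0, with no overlap (Section 2.1.3), so 14 versus 21. PIK3CA alone gives 11 versus 24; KRAS alone gives 3 versus 32.
- Tail after last dose: 21 days, about 0.7 months (Section 9).
- Reference median exposure of 3 months: Section 2.1.2 reports 25% progression-free at 6 months on bevacizumab. If exponential, the median is 6 × ln 2 / ln 4 = 3 months.
- Assumed, because the documents give none: exponential time on drug, the group medians below, and the same event hazard λ of 0.1, 0.2 or 0.3 per month in both groups.
- The two-sided 5% level is also my benchmark; the plan sets none for this comparison.

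**Formula.** With median exposure m, μ = ln 2 / m and tail d, the probability of at least one event is p = 1 − exp(−λd) × μ/(μ + λ). The Fisher rejection rate is the exact sum, over all pairs of counts with Fisher p ≤ 0.05, of the two binomial probabilities multiplied together.

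**Worked case.** λ = 0.1, d = 0.7, so exp(−0.07) = 0.932.
- Median 6: μ = 0.1155; p = 1 − 0.932 × 0.1155/0.2155 = 0.500.
- Median 3: μ = 0.2310; p = 1 − 0.932 × 0.2310/0.3310 = 0.349.
- At 14 versus 21, Fisher's test rejects in 10.5% of trials although the monthly risk is identical.

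**Rejection rates, 14 versus 21, with the tail.**

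| Median months, mutated vs wild type | λ = 0.1 | λ = 0.2 | λ = 0.3 |
|---|---|---|---|
| 3 vs 3 | 3.1% | 3.8% | 3.2% |
| 4 vs 3 | 4.2% | 5.1% | 4.0% |
| 4.5 vs 3 | 5.4% | 6.4% | 4.9% |
| 6 vs 3 | 10.5% | 11.4% | 8.1% |
| 6 vs 2 | 20.1% | 24.1% | 19.5% |

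**Smaller mutated groups.** At 11 versus 24, the range is 6.5-8.6% for 6 vs 3 months and 14.7-18.0% for 6 vs 2. At 3 versus 32 it is 0.5-5.1% and 0.3-9.8%.

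**Early-onset events.** Section 6.1.2 says most diarrhea occurs in the first 3 to 4 weeks. Suppose the hazard is λ in month 1 and 10% of λ afterwards (assumed), so that the cumulative hazard at time t is λ·min(t, 1) + 0.1λ·max(t − 1, 0). Averaged over the same exposure and tail, with λ from 0.1 to 0.5 and 14 versus 21, the test rejects in 2.7-5.8% at 6 vs 3 months and 3.3-7.9% at 6 vs 2.

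**The opposite direction.** Let the mutated group have twice the hazard, 0.2 versus 0.1. With medians of 3 months in both groups, p = 0.534 versus 0.349 and the test rejects in 14.6%. If the mutated group stops earlier, with a median of 1.5 months, p = 0.393 versus 0.349 and rejection falls to 3.7%, no better than the equal-risk rate.

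**Does accounting for exposure help?** Over a common 2-month window at λ = 0.1, p = 1 − exp(−0.2) = 0.181 in both groups, and Fisher's test rejects in 2.1% at 14 versus 21. A simulated log-rank test of time to first event (4,000 trials per setting, no tail) rejects in 5.6-6.1% at 6 vs 3 and 5.1-5.6% at 6 vs 2, close to nominal.

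**The case against.** The strongest case against is that little rests on this comparison. The toxicity objective in Sections 1.3 and 14.1.3 describes the whole cohort, and the mutation objective concerns clinical benefit. Toxicity by mutation appears only in the correlative paragraph and is labelled exploratory. This stands, and it sets the priority.

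It is also objected that the exposure gap is hypothetical. This stands too. A reader might infer that the mutated group will look more toxic. The documents do not support that: Section 8.1 says only that mutations may increase susceptibility, Section 2.2.4 links PIK3CA mutation to resistance to MEK inhibitors, and Sections 5.4 and 6.4.2 end treatment for toxicity. The direction is open, and with equal exposure there is no distortion of this kind.

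A reader might also quote larger figures. Without the follow-up tail, the same calculation gives 11-14% at 6 vs 3 months and 24-30% at 6 vs 2; fixed exposures of 8 versus 2 months give about 50% at 11 versus 24 and λ = 0.1. But the tail is part of the plan, and no figure in the documents supports gaps that wide.

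Finally, a reader might conclude that a log-rank test should replace Fisher's. That goes too far. Progression and toxicity both end treatment, so censoring at treatment stop may be informative, and restricting the test to, say, grade 3 or higher related events would create an endpoint that Section 14.2 does not define. What survives the objections is that nothing in the plan would let a reader separate exposure from risk.

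**Conclusion.** The point holds conditionally. If mutation groups differ in time on drug, the Fisher comparison in Sections 14.2 and 8.6 mixes exposure with risk, in a direction that cannot be known in advance. Under assumed equal constant hazards, the distortion is negligible for a modest exposure gap, two to four times the equal-exposure rejection rate when exposure doubles, and about five to seven times when it triples. It is smaller for early-onset events and for smaller mutated groups. These sizes rest on assumed hazards, exposure distributions and medians.

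It would be wrong to infer that the trial's safety conclusions or its main result are compromised. The primary endpoint, the whole-cohort toxicity description and the monitoring committee's review (Section 12.2) do not use this comparison. It is a low-priority, cheap improvement.

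**What to change.** In Sections 14.2 and 8.6, keep the per-participant tabulation and Fisher's test. For any between-group toxicity comparison, add:

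- time on treatment by group;
- a comparison over a fixed early window common to both groups, for example cycles 1-2, with participants who stopped earlier shown separately; and/or events per participant-month, or time to first event from first dose, censored at the end of one stated adverse-event window, noting that censoring at treatment stop may be informative.

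State that any crude difference will be interpreted only alongside these. The window needs to be named because the documents give two: the final visit at 21 ± 7 days after last dose (Sections 6 and 9) and 30 days after last dose or intervention (Sections 11.4.1 and 11.9). The analysis text should reconcile them.

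The cost is one extra table and some added analysis work. Section 11.9 has event dates recorded, and the medication diaries record dosing dates, so no new data, visits or participants are needed.

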14.3 Sample Size/Accrual Rate

The planned sample size is a maximum of 35 participants. The estimated monthly accrual rate is 2 participants. Participants will be followed for a maximum of 3 years.

14.4 Reporting and Exclusions

14.4.1 Evaluation of Toxicity

All participants will be evaluable for toxicity from the time of their first treatment.

14.4.2 Evaluation of Response

All participants included in the study must be assessed for response to treatment, even if there are major protocol treatment deviations or if they are ineligible. Each participant should be assigned one of the following categories: 1) complete response, 2) partial response, 3) stable disease, 4) progressive disease, 5) early death from malignant disease, 6) early death from toxicity, 7) early death because of other cause, or 9) unknown (not assessable, insufficient data). By arbitrary convention, category 9 usually designates the "unknown" status of any type of data in a clinical database.

All participants who have measurable disease present at baseline, have received at least one cycle of therapy, and have had their disease re-evaluated will be considered evaluable for response. Participants in response categories 5-9 will not be considered evaluable but will remain within the intention to treat analysis.

Participants who develop brain metastasis on study, but continue on study after definitive treatment of their cranial disease, will be considered to have had progressive disease at the point of the diagnosis of the initial brain metastasis.

All conclusions should be based on all evaluable participants. Subanalyses may then be performed on the basis of a subset of participants, excluding those for whom major protocol deviations have been identified (e.g., early death due to other reasons, early discontinuation of treatment, major protocol violations, etc.). However, these subanalyses may not serve as the basis for drawing conclusions concerning treatment efficacy, and the

reasons for excluding participants from the analysis should be clearly reported. The 95% confidence intervals should also be provided.

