4.1 General Guidelines for DF/HCC and DF/PCC Institutions

Institutions will register eligible participants with the DF/HCC Quality Assurance Office for Clinical Trials (QACT) central registration system. Registration must occur prior to the initiation of therapy. Any participant not registered to the protocol before treatment begins will be considered ineligible and registration will be denied.

An investigator will confirm eligibility criteria and a member of the study team will complete the QACT protocol-specific eligibility checklist. Following registration, participants may begin protocol treatment. Issues that would cause treatment delays should be discussed with the Overall Principal Investigator (PI). If a participant does not receive protocol therapy following registration, the participant's registration on the study may be canceled. Notify the QACT Registrar of registration cancellations as soon as possible.

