10.1.1 Definitions

Evaluable for toxicity. All participants who receive at least one dose of study treatment will be evaluable for toxicity from the time of their first treatment.

Evaluable for objective response. Only those participants who have received at least one cycle of therapy, and have had their disease re-evaluated will be considered evaluable for response. These participants will have their response classified according to the definitions stated below. (Note: Participants who exhibit objective disease progression or die due to disease progression prior to the end of cycle 1 will also be considered evaluable.)

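### Section 14.4.2 rests all conclusions on evaluable participants and drops early deaths and unknowns, so the primary response rate and its CI can only hold or rise; Sections 10.1.1 and 14.2 imply different sets

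*Combined protocol and SAP*

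**What the plan says.** Section 14.2 sets the primary aim: "The primary objective of this study is estimation of the best objective response rate (CR + PR) per RECIST 1.1". The test is introduced with "With the planned accrual of 35 participants to this single-arm trial", and "the null hypothesis will be rejected if 5 or more participants respond". It attaches no evaluability condition and names no analysis set.

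Section 14.4.2 gives every participant a response category. Categories 1 to 4 are CR, PR, stable disease and progression. Categories 5 to 7 are early death from malignant disease, from toxicity and from another cause. Category 9 is unknown, and no category 8 is listed. Participants with measurable disease at baseline who "have received at least one cycle of therapy, and have had their disease re-evaluated will be considered evaluable for response". It then says "Participants in response categories 5-9 will not be considered evaluable but will remain within the intention to treat analysis" and, two paragraphs later, "All conclusions should be based on all evaluable participants".

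Section 10.1.1 has a similar one-cycle and re-evaluation rule but adds an exception: "Participants who exhibit objective disease progression or die due to disease progression prior to the end of cycle 1 will also be considered evaluable".

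**The concern.** The primary result is an estimate from a single arm, read against an external rate of 7%. A participant who dies early of her disease or of toxicity has not benefited, yet Section 14.4.2 takes her out of the denominator on which conclusions rest. The intention-to-treat analysis that keeps her is mentioned once, is not defined, and is given no part in any conclusion.

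The sections also disagree. A participant who dies of progression in cycle 1 is in the denominator under Section 10.1.1 and out of it under Section 14.4.2. The sample size calculation in Section 14.2 is consistent with all 35 being counted. Two analysts following different sections could report different primary rates and intervals from the same data.

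**Working it through.** **Inputs.** From Section 14.2: N = 35, null rate 0.07, alternative 0.22, one-sided exact binomial test at 0.09, rejection at 5 or more responders, stated power 91%. Section 14.4.2 asks for 95% confidence intervals without naming a method; Clopper-Pearson is assumed. No unevaluable rate is given, so 0, 3, 5 or 7 of 35 are assumed unevaluable.

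**Step 1: the plan's own figure.** With X binomial on 35:

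- power = P(X ≥ 5 | 35, 0.22) = 0.910, which matches the stated 91%
- type I error = P(X ≥ 5 | 35, 0.07) = 0.095

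Cutoffs of 4 or 6 give power 0.966 or 0.813, so of these only 5 of 35 reproduces the stated power. That supports reading Section 14.2 as counting all 35.

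**Step 2: direction.** Categories 5 to 9 hold no CR or PR. Removing them leaves the responder count x unchanged and reduces the denominator from 35 to n. The estimate becomes x/n = (x/35) × (35/n), and 35/n is at least 1. For x > 0 both Clopper-Pearson limits rise as n falls.

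**Step 3: size with five responders.**

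| Unevaluable (assumed) | n | Rate | 95% CI |
|---|---|---|---|
| 0 | 35 | 5/35 = 14.3% | 4.8 to 30.3 |
| 3 | 32 | 5/32 = 15.6% | 5.3 to 32.8 |
| 5 | 30 | 5/30 = 16.7% | 5.6 to 34.7 |
| 7 | 28 | 5/28 = 17.9% | 6.1 to 36.9 |

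**Step 4: expected reading of a given true rate.** If all those excluded are non-responders, a true all-treated rate p reads as p × 35/n:

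| n | p = 7% | p = 22% |
|---|---|---|
| 35 | 7.0% | 22.0% |
| 32 | 7.7% | 24.1% |
| 30 | 8.2% | 25.7% |
| 28 | 8.75% | 27.5% |

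**Step 5: the interval against the 7% null.** With six responders, 6/35 = 17.1% (6.6 to 33.7) includes 7%, while 6/32 = 18.8% (7.2 to 36.4) excludes it. Three exclusions change how the interval reads. This happens only at six responders within the assumed range: with five, the lower limit is still 6.1% on 28, and with seven it is already 8.4% on 35.

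**Step 6: the decision rule.** Excluding non-responders does not alter the responder count, so the decision at 5 or more, its power of 0.910 and its type I error of 0.095 are unchanged. This would fail only if someone re-derived the cutoff on the evaluable number, which the plan does not propose. Allowing the same rounding of alpha to 0.09, that cutoff would drop to 4 at n = 25 or fewer.

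**The case against.** The strongest case is that Section 14.4.2 is ambiguous rather than plainly exclusionary. Its last paragraph lists early death from other reasons and early discontinuation as grounds for exclusion in subanalyses, and bars those subanalyses from supporting efficacy conclusions. Such participants can be removed in a subanalysis only if they were in the main set. This shows a further inconsistency, but it does not override the explicit sentence on categories 5-9.

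Several other points stand as limits:

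- Every participant is categorised, so an all-participant rate can always be computed. What is missing is a definition of that analysis and its priority.
- The go/no-go decision is unaffected.
- The largest shift shown for five responders is 17.9 − 14.3 = 3.6 percentage points, against an interval about 25 points wide, and the size rests on an assumed unevaluable rate.
- Entry requires measurable disease and a life expectancy above 3 months. The Section 9 calendar also schedules a disease assessment at the off-treatment visit, which covers many who stop before the first even-cycle scan. It cannot cover those who die first, and a participant with less than one cycle stays unevaluable under Section 14.4.2 even if rescanned.
- The denominators behind the 7% historical rate are not given, so the documents cannot show whether an evaluable-only rate would be the like-for-like comparison.
- That Section 14.2 means all 35 is an inference from its wording and from the reproduced power.

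None of these settles which denominator is primary or reconciles Section 10.1.1 with Section 14.4.2.

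**Conclusion.** The concern holds. Followed as written, Section 14.4.2 removes treatment failures and unknowns from the primary estimate, and removing those categories can only leave the rate and its interval unchanged or raise them. The inflation factor is 35/n: none if everyone is evaluable, 35/32 = 1.09 with three unevaluable and 35/28 = 1.25 with seven. These counts are assumptions, as is the Clopper-Pearson method. In theory the one-cycle condition could drop a responder and act the other way, but with scans every two cycles this is remote.

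The effect is on the reported estimate and interval, and on which of two conflicting evaluability definitions an analyst applies. It is not on the decision at five responders. It should be fixed before analysis.

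**What to change.** - In Sections 14.2 and 14.4.2, define the primary response rate as confirmed CR plus PR divided by all participants who start study treatment. Section 4.1 already allows for those never treated: "If a participant does not receive protocol therapy following registration, the participant's registration on the study may be canceled". Because that cancellation is optional, the text should state the treated set explicitly and not rely on it.
- Count categories 5-9 as non-responders, and say that for category 9 this is a conservative convention.
- Apply the five-responder rule and the 95% confidence interval to that set, and replace the sentence that bases all conclusions on evaluable participants.
- Report the evaluable-only rate as a labelled sensitivity analysis.
- Make the evaluability definitions in Sections 10.1.1 and 14.4.2 agree, including the treatment of progression or death from progression before the end of cycle 1.

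The cost is wording in three sections. No extra data are needed, because every participant is already assigned a category. The reported rate may be slightly lower.
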